#### *Cardiovascular performance: Oxygen consumption measurements*

Study participants will complete the treadmill exercise respirometry at their first study visit. This exercise will also be performed on within 24 to 48 hours of the final hot tub experience. This waiting period will obviate the transient enhancements of cardiac output and systemic vascular resistance due to water immersion that may alter  $VO_{2max}$  assessments. These effects are normalized shortly after removal from the water and heat sources, thus should be normalized and not have impact on  $VO_{2max}$  by this time. This waiting period also allows for muscle rest prior to the exercise step test. Importantly, waiting until the next day to perform the laboratory and exercise testing also ensures that the changes seen are not acute benefits of heat therapy, but are chronic.

#### **Measurements:**

The following data will be collected at two separate time points: T1 = beginning of the study, prior to hot water immersion; and T2 = at the end of the study, 24-48 hours after the last hot tub experience.

1. Blood pressure, stroke volume, stroke volume variation, cardiac index and systemic vascular resistance, heart rate with the ClearSight® (Edwards Lifesciences, Irvine, CA) monitor
2.  $VO_2$  as measured with treadmill exercise respirometry
3. Blood collection tube of approximately 4 tablespoons of blood to assess complete blood count, complete metabolic panel, lipid panel, and serum heat shock protein measurements (Hsp72 and Hsp90)

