### *Study Cohort and Safety*

Twenty adults, age 50 or older, will be included in the study. Demographic data required for pertinent calculations will be obtained from each participant including height, weight, age and gender. Exclusion criteria includes current major cardiovascular disease known to the patient including recent myocardial infarction, stroke, angina pectoris, high grade coronary vasculopathy or atherosclerosis, severe valvular disease, current cardiac dysrhythmia that requires treatment (i.e. atrial fibrillation, atrial flutter, frequent ventricular premature beats and/or implantation of permanent pacemaker/defibrillator). Patients with a history of coronary artery bypass grafting, valvular surgeries and coronary interventions will be assessed as to current exercise tolerance and symptomology. Other exclusion criteria include current treatment with steroids or immunosuppressive agents, current malignancy, serious liver disease, end-stage renal disease or judgement by a medical provider that water or heat therapy poses an undue burden or risk upon the individual. All females of child bearing age will consent to pregnancy testing and will be excluded if pregnant. Should a participant become hemodynamically or cognitively impaired during any portion of the study activities, 911 will be called for evaluation and possible transport to the emergency department at TUKH. Volunteers can choose to recuse themselves from any or all of the study activities at any time.

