### *Hot Water Immersion Therapy*

Previous reports have demonstrated that benefits from heat therapy require 5-14 days to become apparent. Thus, participants in the present study will undergo 8-10 shoulder-high hot water immersions of 40.5°C for 45 minutes/session during a 14-16-day period. Either 1) a rectal probe with sterile disposable sheaths or 2) a sterile rectal thermistor probe will be used to monitor the subject's temperature ( $T_{re}$ ). These probes are inserted approximately 2.54 cm past the anal sphincter. The subject will be removed from the hot tub if  $T_{re}$  is 38.5°C or higher. Participants will be asked to sit on a bench of the hot tub with until  $T_{re}$  is < 38.0°C at which time they may return to the hot tub. Participants are able to drink water *ad libitum* while in the hot tub.  $T_{re}$  will be monitored for 10 additional minutes following emersion from the hot tub or until  $T_{re}$  < 38.0°C.

Hot tub located in the CRC at KUMC.

Subjects will have dry weights measured prior to and after hot water therapy. If body weight loss following therapy is > 1%, the participant will be asked to drink additional fluids to make up the difference. Heart rate will be monitored continuously during heat therapy. If heart rate is altered > 50% from baseline, the participant will

be assessed for neurologic and hemodynamic changes. If there are changes concerning these assessments, the subject will be removed from the hot tub, temperature monitored, and a medical provider notified. Blood pressure will be obtained prior to and after hot water therapy. Participants with pre-therapy systolic blood pressure < 75mmHg or > 180mmHg and/or diastolic blood pressure < 40mmHg or > 90mmHg, will not be allowed to participate in hot water therapy. If post-hot tub blood pressure varies by > 20% lower or > 30% higher than baseline values, the subject will be monitored until return to < 20% deviation from baseline. If blood pressure values do not return to baseline after 10 minutes, discussion with a medical provider will take place prior to discharge from CTSU. If at any time, should a participant become hemodynamically or cognitively impaired during any portion of the study activities, 911 will be called for evaluation and possible transport to the emergency department at TUKH.

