#### **Risks:**

##### *Whole-Body Heat Therapy:*

There are some risks associated with heat exposure, including: fatigue, light-headedness, muscle cramps, dehydration, and neurological detriments (i.e. heat stroke). However, these symptoms do not typically occur until core temperature rises above 40°C. Core temperature (rectal thermistor) will be continuously monitored and recorded. Subjects will be removed from the hot bath immediately if either core temperature reaches 39.5°C or the subjects experience any symptoms of heat-related illness. All symptoms subside upon lowering core temperature. Ice packs will be on hand if rapid cooling is necessary (see Rapid Cooling SOP). Heart rate will also be continuously monitored and recorded throughout heating. If HR increases > 60 beats/min above resting or increases > 20 beat/min with a 5 min time period, subjects will be moved to a seated position if they were previously fully submerged, or removed from the hot tub if they were already sitting up. Additionally, heat exposure may have detrimental effect on a developing fetus in females. Thus, subjects who are pregnant or trying to conceive will be excluded from the study. This will be confirmed with a pregnancy test.

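### The next-day wait before T2 does not rule out plasma-volume or draw-condition shifts in Hsp72, Hsp90 and lipids: standardise the draw and add a correction from the blood count already taken

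*Protocol*

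**What the plan says.** **Design.** Study Cohort and Safety: "Twenty adults, age 50 or older, will be included in the study". No comparison group is described.

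**Exposure.** Hot Water Immersion Therapy: participants have "8-10 shoulder-high hot water immersions of 40.5°C for 45 minutes/session during a 14-16-day period". On fluids: "Participants are able to drink water *ad libitum* while in the hot tub", and "If body weight loss following therapy is > 1%, the participant will be asked to drink additional fluids to make up the difference". The risk section on whole-body heat lists "fatigue, light-headedness, muscle cramps, dehydration, and neurological detriments (i.e. heat stroke").

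**Sampling.** Measurements: "T1 = beginning of the study, prior to hot water immersion; and T2 = at the end of the study, 24-48 hours after the last hot" tub session. At both times blood is taken "to assess complete blood count, complete metabolic panel, lipid panel, and serum heat shock protein measurements (Hsp72 and Hsp90"). The complete blood count, which supplies haemoglobin and haematocrit, therefore comes from the same draw as the markers.

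**Interpretation.** The section on oxygen consumption measurements says of laboratory and exercise testing alike that the next-day wait "ensures that the changes seen are not acute benefits of heat therapy, but are chronic".

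**What is not stated.** The protocol gives no posture or hydration state for the draw. It gives no order of blood draw and treadmill test within a visit. It does not say how any blood marker will be analysed.

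**The concern.** Hsp72, Hsp90 and the lipids are measured as amounts per volume. If plasma volume at T2 differs from that at T1, the reading changes although the circulating amount may not have. Two routes are open under the present text:

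- **A lasting plasma-volume change** after repeated heat. By definition it would outlast a 24-48 hour wait, so the wait cannot exclude it.
- **Unequal draw conditions.** A T1 draw before the treadmill test and a T2 draw after it, or one seated and one supine, would both comply with the protocol. Either could shift concentrations.

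With one group, a shift shared by participants cannot be separated from a marker response. Direction matters. Plasma expansion would mimic a fall in lipids and hide a rise in heat shock proteins; contraction would do the reverse.

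The markers are not incidental. The Objectives section sets out to relate molecular mechanisms to functional improvement, the Background names heat shock proteins as a major mechanism, and Hsp72 and Hsp90 are the only such proteins measured. Blood volume is also a rival explanation for changes in stroke volume and cardiac index, which the Study Aim section attributes to vascular tone.

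**Working it through.** The protocol states no effect size, standard deviation, power or sample-size calculation, so there is no figure to reproduce. What follows illustrates scale. **From the documents:** n = 20, paired T1 and T2 values, and a draw of about 4 tablespoons. **Assumed:** everything else.

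**1. Dilution at constant circulating mass.** C2/C1 = 1/(1 + d), where d is the fractional change in plasma volume.

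| d (assumed) | Change in concentration |
|---|---|
| -5% | 1/0.95 - 1 = +5.3% |
| +3% | 1/1.03 - 1 = -2.9% |
| +5% | 1/1.05 - 1 = -4.8% |
| +10% | 1/1.10 - 1 = -9.1% |

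**2. Recovering d from the blood count (Dill-Costill).** PV2/PV1 = (Hb1/Hb2) × (1 - Hct2)/(1 - Hct1).

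Invented example: haemoglobin 14.0 to 13.4 g/dL and haematocrit 42.0% to 40.2%. Then (14.0/13.4) × (0.598/0.580) = 1.045 × 1.031 = 1.077, so plasma volume is up 7.7%. Concentration changes by 1/1.077 - 1 = -7.2%, and an LDL of 130 would read about 121 with no true change. This example lies towards the upper end of the assumed range.

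As a check, start from Hb 14 g/dL and Hct 0.42 with red-cell mass held constant. Plasma-volume ratios of 0.95, 1.03, 1.05 and 1.10 are all returned exactly by the formula.

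**3. Could such a shift be declared significant?** Paired two-sided 5% t test, n = 20, no change in marker mass, shift log(1 + d) on the log scale. Noncentrality = log(1 + d)/(SD/√20), with 19 degrees of freedom. Probability of p < 0.05:

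| d | SD of log change 0.10 | 0.20 | 0.30 |
|---|---|---|---|
| 3% | 0.241 | 0.096 | 0.070 |
| 5% | 0.544 | 0.179 | 0.106 |
| 10% | 0.981 | 0.525 | 0.271 |

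The nominal value is 0.05. The distortion is material for low-variability markers or a large shift, and small for noisy markers when the shift is 3-5%.

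**4. Limit of the correction.** Writing M for red-cell mass, the formula returns (M1/M2) × (true PV2/PV1), so it is exact only if M is stable. Four tablespoons is about 59 mL. With an assumed 5 L blood volume, 59/5000 = 1.2% of red cells are removed at T1. If none were replaced by T2, the formula would read 1/0.988 - 1 = +1.2% plasma volume with no true change.

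**The case against.** The other side has a good deal of weight.

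- **The analysis is not stated.** A reader might infer that the markers will be compared as raw concentrations and the blood count used only as another outcome. The protocol says neither. A correction formula could sit in a statistical analysis plan that is not shown, and the data for it are already collected. This stands. The draw conditions are different: once samples are taken under unequal conditions, no later plan can repair them.
- **Session fluids are remote from the draw.** A reader might infer from the drinking, weight-replacement and dehydration text that fluid state differs systematically, in one direction, between T1 and T2. The documents do not support that. Those procedures limit net loss, and T2 comes 24-48 hours later. The risk section adds that such symptoms usually appear only above a core temperature of 40°C, and both removal temperatures in the protocol (38.5°C and 39.5°C) are lower. What remains is a possible lasting shift of unknown size and sign.
- **A lasting shift is itself not acute.** This is true. But the sentence claims chronic benefit, and a dilution effect on a concentration is not evidence of benefit.
- **The corrected value need not be the main reading.** Lipids are read clinically as concentrations, and regulated quantities in the metabolic panel, such as electrolytes and glucose, need not follow constant-mass dilution. This stands and limits the remedy to a sensitivity analysis for Hsp72, Hsp90 and lipids.
- **This is a small pilot.** No blood marker is named as primary. That lowers the weight of the point but does not remove it.

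**Conclusion.** The point holds in a limited form. The wait before T2 separates acute from later effects. It does not ensure that a change in a blood concentration is a chronic benefit, because a lasting plasma-volume change or unequal draw conditions could produce the same reading in an uncontrolled before-after comparison.

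The possible size is +5.3% to -9.1% in concentration, resting on an assumed plasma-volume change of -5% to +10% at constant circulating mass. The documents give no value or direction, so this is a range of what could happen and not an estimate of what will.

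A reader might also infer that VO2 is mismeasured. It is not: a change in blood volume would bear on why VO2, stroke volume or cardiac index changed, not on whether the value is correct. The improvement is worthwhile and cheap. Standardising the draw is the part that must be settled before participants are sampled.

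**What to change.** In the Measurements section:

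1. Require the T1 and T2 blood draws in the same posture and before the treadmill test.
2. State that each participant's T1-to-T2 plasma-volume change will be calculated from the haemoglobin and haematocrit in the complete blood count (Dill-Costill formula).
3. Report Hsp72, Hsp90 and lipids raw, with a plasma-volume-corrected sensitivity analysis.
4. Report the plasma-volume change beside stroke volume, cardiac index and VO2 as an aid to interpretation.

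In the section on oxygen consumption measurements, replace the assurance about chronic benefit with wording that the wait reduces the influence of acute effects.

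**Cost.** A few sentences, one derived variable and a fixed order of procedures at two visits, with no new sample. Measurement error in haemoglobin and haematocrit adds some noise to corrected values. The correction assumes stable red-cell mass; the T1 draw removes about 1.2% of it (assuming 5 L blood volume), which should be noted when small corrected changes are read.

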#### **Risks:**

##### *Whole-Body Heat Therapy:*

There are some risks associated with heat exposure, including: fatigue, light-headedness, muscle cramps, dehydration, and neurological detriments (i.e. heat stroke). However, these symptoms do not typically occur until core temperature rises above 40°C. Core temperature (rectal thermistor) will be continuously monitored and recorded. Subjects will be removed from the hot bath immediately if either core temperature reaches 39.5°C or the subjects experience any symptoms of heat-related illness. All symptoms subside upon lowering core temperature. Ice packs will be on hand if rapid cooling is necessary (see Rapid Cooling SOP). Heart rate will also be continuously monitored and recorded throughout heating. If HR increases > 60 beats/min above resting or increases > 20 beat/min with a 5 min time period, subjects will be moved to a seated position if they were previously fully submerged, or removed from the hot tub if they were already sitting up. Additionally, heat exposure may have detrimental effect on a developing fetus in females. Thus, subjects who are pregnant or trying to conceive will be excluded from the study. This will be confirmed with a pregnancy test.

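### The protocol gives two different rectal temperatures for taking a participant out of the hot tub, 38.5°C and 39.5°C, and does not say which governs

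*Protocol*

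**What the plan says.** The Methods section, under Hot Water Immersion Therapy, sets out the session: shoulder-high immersion at 40.5°C for 45 minutes, 8 to 10 times over 14 to 16 days. Rectal temperature is followed with a sheathed rectal probe or a thermistor ("a sterile rectal thermistor probe will be used to monitor" it).

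The removal rule there is: "The subject will be removed from the hot tub if" rectal temperature "is 38.5°C or higher. Participants will be asked to sit on a bench of the hot tub with until" it is below 38.0°C, "at which time they may return to the hot tub". After the session, rectal temperature "will be monitored for 10 additional minutes following emersion from the hot tub or until" it is below 38.0°C.

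The Risks section, under Whole-Body Heat Therapy, covers the same sessions. It notes that "these symptoms do not typically occur until core temperature rises above 40°C" and states the measurement: "Core temperature (rectal thermistor) will be continuously monitored and recorded". Its removal rule is: "Subjects will be removed from the hot bath immediately if either core temperature reaches 39.5°C or the subjects experience any symptoms of heat-related illness". It adds ice packs, a Rapid Cooling SOP and a stepped response to a rise in heart rate.

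Neither section refers to the other's temperature limit, and no other part of the protocol reconciles them.

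**The concern.** A removal limit is an instruction that staff must apply at once, at the tub side. Here it has two values for the same kind of measurement in the same session. From 38.5°C up to 39.5°C the procedure requires the participant to come out, while the temperature criterion in the Risks section does not yet ask for it.

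Participant safety is the main stake. The cohort is aged 50 or older, and the water at 40.5°C is hotter than either limit, so the bath itself does not hold core temperature below them. The Risks section is also where staff would look for heat-illness limits, because the symptom trigger and the cooling measures are there. The symptom trigger does not fully close the gap: by the protocol's own account, symptoms typically appear only above 40°C, so a participant between the two limits would often have none.

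The second stake is consistency of treatment. Heat exposure is the intervention, and in a session that reaches 38.5°C the heating delivered would depend on which rule the staff member followed.

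**Working it through.** This is a comparison of two stated rules. It involves no sample size, power or error rate, and the protocol gives no derived figure to reproduce.

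**Inputs, all from the protocol**

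| Item | Hot Water Immersion Therapy | Risks: Whole-Body Heat Therapy |
|---|---|---|
| Measure | rectal (probe or thermistor) | core, by rectal thermistor |
| Action | removal from the tub | immediate removal from the tub |
| Temperature trigger | 38.5°C or higher | 39.5°C |
| Other trigger in the same rule | none | any symptom of heat-related illness |
| Return rule | allowed below 38.0°C | none stated |
| Level above which symptoms are expected | not stated | 40°C |

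**Step 1: do the rules concern the same thing?** Yes. Both use a rectal reading, both apply during immersion, and both say the participant is removed. A difference in measurement site therefore does not explain the two numbers.

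**Step 2: gap between the limits.** 39.5 − 38.5 = 1.0°C.

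**Step 3: margin to the protocol's own 40°C.**
- At 38.5°C: 40 − 38.5 = 1.5°C.
- At 39.5°C: 40 − 39.5 = 0.5°C.
- Ratio: 0.5 / 1.5 = 1/3.

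**Step 4: distance to the 38.0°C return and post-session level.**
- From 38.5°C: 38.5 − 38.0 = 0.5°C.
- From 39.5°C: 39.5 − 38.0 = 1.5°C, three times as far to cool.

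**Step 5: is a two-tier scheme written down?** No. Under such a scheme, 38.5°C would mean a pause and 39.5°C the end of the session. The Risks section attaches no such consequence to 39.5°C. It does write out steps for heart rate (sit up if fully submerged, leave the tub if already seated), but none for temperature. If the 38.5°C rule is followed and the participant is out of the water, 39.5°C could be reached only by a continued rise after leaving or by a missed removal, so a removal rule at that level would have almost no use.

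**Step 6: how many sessions?** Twenty participants with 8 to 10 sessions each give 20 × 8 = 160 to 20 × 10 = 200 planned sessions. Only those reaching 38.5°C are affected. No warming rate is given, so that share is unknown.

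**The case against.** The strongest reply is that the rules are not logically incompatible. Each is a sufficient condition for removal, and the Risks section does not say that 39.5°C is the only trigger or that staying in between the limits is permitted. Staff who follow the whole protocol act at 38.5°C. This is correct, and it limits the fault: harm requires someone to work from one section without the other. The protocol nevertheless leaves staff to infer that the stricter limit governs.

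A two-step intention is also plausible. The first rule is mild and reversible (sit on the bench, return when cooler); the second is immediate and stands beside symptoms, ice packs and the cooling SOP. The text also does not say whether the bench is out of the water. If it is partly submerged, temperature could keep rising and a 39.5°C backstop would have a purpose. This reading cannot be excluded, but the tiers are not written. If they were intended, the point becomes that they must be stated, together with where the participant sits.

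The heart-rate rules in the two sections also differ. They set different triggers for different responses: a change above 50% from baseline prompts an assessment, whereas a rise above 60 beats/min over resting, or above 20 beats/min within 5 minutes, prompts a change of position or removal. They can run side by side. The temperature rules set two values for what is written as the same response.

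Three further limits stand. The one-third margin restates the 1.0°C gap and is not an estimate of risk. Even 39.5°C is below the 40°C the protocol cites, any symptom prompts removal at any temperature, and monitoring is continuous. The Rapid Cooling SOP is not available here and might address the limit, although the protocol cites it only for cooling.

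**Conclusion.** The concern holds. The protocol states two removal temperatures 1.0°C apart for rectal temperature in the same sessions, without tiers or precedence. The higher value leaves 0.5°C below the protocol's own 40°C, against 1.5°C for the lower.

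This is an inconsistency in a safety instruction that should be fixed. It is not an error in the sample size or the analysis, and it does not show that any participant would be kept in to 39.5°C. The possible effect on heat delivered is confined to sessions reaching 38.5°C, whose number is unknown, and arises only if staff use the higher limit. The conclusion rests on the protocol text alone and assumes that no document outside it, such as the cooling SOP, settles which limit applies.

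**What to change.** Preferred: in the Risks section, replace 39.5°C with 38.5°C, add the same return rule (below 38.0°C), and keep the removal for any symptom of heat-related illness.

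If two tiers are intended, write both in both sections:
- at a rectal temperature of 38.5°C or higher, leave the water and stay out until below 38.0°C;
- at 39.5°C, or at any symptom of heat-related illness, end the session.

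In either case, say plainly that the bench used for cooling is out of the water. The heart-rate rules need no change in substance; listing them together would be enough.

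The cost is a wording amendment of one or two sentences. No new equipment or measurement is needed, because core temperature is already monitored and recorded continuously.
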